All skin swab samples will be stored at -80 °C until further processing. CoreBiome will receive skin swabs (with subject ID only, no other PHI), they will extract DNA, and perform 16S rRNA gene and/or shotgun metagenomic sequencing. Corebiome will send the BIDMC research team the raw data. The research team will be doing the bioinformatics/analysis, not CoreBiome. If, after sending the skin swabs, subject withdraws, then the PI will ask Corebiome to destroy the sample and they will not perform DNA extraction or 16S rRNA/shotgun metagenomic sequencing.

Control Group:

Procedures and Measurements	Visit 1	Visit 2
Procedures and Measurements	Screening Day 0	Day 120 +/- 5 days
Informed Consent, HIPPA Auth, Photo Release	X	
Review Inclusion/Exclusion Criteria	X	
Review of Demographics	X	
Review of Medical/Surgical Histories	X	X
Review of Current Medications	X	X
Physical Examination of Unaffected Skin	X	X
Regular Photography	X	X
Skin Swabs	X	X
Assess for Adverse Events	X	X

Experimental Group:

Procedures and Measurements	Visit 1	Visit 2	Visit 3
Procedures and Measurements	Screening Day 0	Day 90 +/- 5 days	Day 120 +/- 5 days
Informed Consent, HIPPA Auth, Photo Release	X		
Review of Inclusion/Exclusion Criteria	X		
Review of Demographics	X		
Review of Medical/Surgical Histories	X	X	X
Review of Current Medications	X	X	X
Review of Acne Histories	X		
Review of Past/Current Acne Medications	X		
Physical Examination of Acne Skin	X	X	X
Acne Leeds Score	X	X	X
Acne PGA Score	X	X	X
Regular Photography	X	X	X
Skin Swabs	X	X	X
Assess for Adverse Events	X	X	X

Data Analysis

Primary Study Parameter(s): The primary outcome of this study is assessing for changes in skin microbial composition in acne patients after treatment with Altreno or BPO by specifically comparing their skin microbiomes (1) at baseline, (2) after 3 months of treatment, and (3) 1 month 10 after discontinuation of treatment. Comparisons of species diversity and relative abundance of the identified species will be made across healthy controls, Altreno group, and BPO group.

The raw sequencing data will be first processed into taxonomic features using the standardized DADA2 protocol as implemented in the bioBakery. Then, we will analyze the

three available microbial features (taxa, alpha diversity summary statistics, and community structure via beta diversity) across the three groups defined above.

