Secondary Study Parameter(s): The clinical severity will also be correlated to the presence and/or dominance of *P. acnes* and other populations using the following measures:

- **Physician Global Assessment of Acne:** Categorical variable. A chi-square test will be performed for analysis.
- **Leeds Acne Score:** Ordinal variable. A correlation analysis and depending on distribution, one-way ANOVA, a Kruskal Wallis or a Wilcoxon rank sum test will be performed for analysis.

Other Study Parameter(s): Patient characteristics and demographics data will be presented using descriptive statistics. At every visit, adverse events and changes in medications will be registered.

Statistical Analysis Plan (per Diversigen, who performed computational analysis)

“To examine differences in abundance for taxa between treatment groups and across time, we examined taxa abundances at the Phylum, Family, Genus and ASV levels using the ASV count table as inputs. At each level of interest, count abundances were aggregated then transformed using the centered log ratio (CLR) transformation as implemented in the ALDEx2 R package. Briefly, transformation was performed using the `aldex.clr()` function, which estimates sequencing technical variation using Monte-Carlo sampling ($n = 128$) and generates CLR-transformed tables for each instance. A median CLR value for each taxon across all MC instances calculated and used for downstream plotting purposes.

Next, we performed differential abundance testing using LME models of the following model:

- `taxon_abundance ~ Treatment_Cohort*Timepoint + (1|SubjectID)`

Pairwise contrast p-values for all relevant Treatment_Cohort and Timepoint comparisons were extracted from the model using `emmeans()`. Next, p-values were corrected for multiple hypothesis correction across all taxa tested using the FDR method. Finally, all adjusted p-values generated by testing were averaged across all 128 MC instances to obtain a `padj` value for each taxon for each pairwise comparison of interest.

Using our standard significance thresholds of $padj < 0.05$, we found no taxa as significantly different in abundance at any level in any of the pairwise comparisons we examined. Therefore, we relaxed our threshold to $padj < 0.2$, which is less conservative but has been reported in the literature. Under this threshold, we found a few taxa that were significantly different.”

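### The cut-off was moved from padj 0.05 to 0.2 because nothing passed 0.05, and the taxa then found are called significant

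*Combined protocol and SAP*

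**What the plan says.** The Statistical Analysis Plan (per Diversigen) describes mixed-model testing of CLR-transformed abundances at four taxonomic levels: "we examined taxa abundances at the Phylum, Family, Genus and ASV levels using the ASV count table as inputs". On multiplicity it says that "p-values were corrected for multiple hypothesis correction across all taxa tested using the FDR method". The adjusted values are then averaged over 128 Monte Carlo instances to give one `padj` per taxon and comparison.

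The results follow in three consecutive statements:

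1. "Using our standard significance thresholds of $padj < 0.05" (the analyst's default), "we found no taxa as significantly different in abundance at any level in any of the pairwise comparisons we examined".
2. "Therefore, we relaxed our threshold to $padj < 0.2$, which is less conservative but has been reported in the literature".
3. "Under this threshold, we found a few taxa that were significantly different".

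The Data Analysis section, under Primary Study Parameter(s), makes change in skin microbial composition the primary outcome and adds: "Comparisons of species diversity and relative abundance of the identified species will be made across healthy controls, Altreno group, and BPO group". That section sets no significance threshold, neither 0.05 nor 0.2, and no rule for changing one.

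**The concern.** The first word of the second statement gives the reason for the change: the cut-off moved because the list was empty. The only support offered is that others have used 0.2, with no source. Use elsewhere does not make a threshold confirmatory here when it was chosen after these data were seen.

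Relative abundance is a named part of the primary outcome. Under the standard applied first, that part is null at every level and contrast examined. A reader who keeps only the last statement takes away the opposite. The taxa have not been shown to be chance findings, but a rule adopted after an empty list cannot support calling them significant.

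**Working it through.** The document states no power, overall error rate or sample-size derivation, so there is no plan figure to reproduce. The check is what the change of cut-off does to the chance of a false call.

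**Inputs from the Statistical Analysis Plan:** cut-offs 0.05 and 0.2; FDR adjustment across taxa; `padj` as the mean adjusted p-value over 128 instances; four taxonomic levels.

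**Not given, so assumed:** Benjamini-Hochberg as the FDR method; the number of taxa per family; the correlation between taxa; the agreement between Monte Carlo instances; the number of FDR families; the number of taxa meant by a few.

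**Step 1. Nominal level.** 0.20 / 0.05 = 4. If 3, 5 or 10 taxa were found, the nominal expected number of false ones at 0.2 is up to 0.2 × 3 = 0.6, 0.2 × 5 = 1 or 0.2 × 10 = 2.

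**Step 2. One family, no true differences, independent p-values, no averaging.** Here P(any call at level q) = q, so 0.05 and 0.20.

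- P(call at 0.2, given none at 0.05) = 1 − 0.80/0.95 = 0.158.
- Two-step rule (0.05 first, 0.2 if empty): 0.05 + 0.95 × 0.158 = 0.20.

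The two-step rule has the same total as using 0.2 from the start, so testing first at 0.05 gives no protection.

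**Step 3. Simulation check of step 2.** 200,000 null replicates, two-sided z tests, 6, 25, 50 or 150 taxa in the family:

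| Taxa | Any call at 0.05 | Any call at 0.2 | Call at 0.2 given none at 0.05 |
|---|---|---|---|
| Independent | 0.049–0.052 | 0.199–0.200 | 0.157–0.158 |
| Sum to zero, as with CLR | 0.049–0.050 | 0.193–0.200 | 0.151–0.158 |
| Assumed equal correlation 0.3 | 0.043–0.048 | 0.154–0.187 | 0.115–0.146 |

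**Step 4. Averaging adjusted p-values over 128 instances.** One family of 50 independent null taxa, 1,500 runs. The last column is (second − first) / (1 − first).

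| Assumed between-instance correlation | Any call at 0.05 | Any call at 0.2 | Call at 0.2 given none at 0.05 |
|---|---|---|---|
| 0.95 | 2.4% | 13.7% | 11.3/97.6 = 0.12 |
| 0.8 | 0.3% | 5.5% | 5.2/99.7 = 0.05 |
| 0.5 | about 0% | 0.1% | about 0.001 |

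Further runs with 50 taxa and correlation 0.95 gave up to 3.2% and 16.7%.

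**Step 5. Several independent families, no averaging.** P(any call) = 1 − (1 − q)^k.

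- k = 4 (one per level): 18.6% at 0.05, 59.0% at 0.2.
- k = 14: 51.2% and 95.6%.
- k = 56 (14 × 4): 94.3% and over 99.9%.

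The 14 is an assumed count of contrasts from the visit schedule. Within cohorts over time there are 1 + 3 + 3 = 7. Between cohorts at the same visit there are 3 + 1 + 3 = 7. Levels and contrasts overlap, so independence is a simplification.

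Steps 4 and 5 pull in opposite directions. In every scenario 0.2 gives the higher rate.

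**The case against.** The strongest reply is that nothing is hidden. The same paragraph reports the null at 0.05, says the threshold was relaxed, calls it less conservative and ties the positive statement to that threshold. An FDR of 0.2 is defensible in exploratory work, and the study did not prespecify 0.05 either. All of this is true and removes any suggestion of concealment. It does not justify the word significant: 0.05 was the analyst's declared standard and was applied first, and the text does not label the 0.2 results exploratory.

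On size, the 0.05, 0.20 and 0.158 figures omit the averaging that was actually done, which can reduce them sharply (step 4). That stands, as does the opposite effect of several families. The 20% must not be quoted as the actual false-discovery share in this study.

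The two-step result follows by construction, since anything below 0.05 is also below 0.2. It therefore shows no error beyond that of a fixed 0.2. What it does show is that the first look at 0.05 cannot be credited as a safeguard.

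The primary outcome refers to species, whereas the levels tested are phylum, family, genus and ASV, so the correspondence is imperfect. These are nevertheless the only abundance tests described. Finally, the passage is a quotation from the vendor, so the study team may have to add a statement or obtain a revised report instead of editing the words.

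**Conclusion.** The concern holds and must be fixed. The threshold was changed because of the result, without a prespecified rule, and the taxa so obtained are called significant on a component of the primary outcome. By the standard applied first, the differential-abundance result is zero significant taxa at the four levels and in all contrasts examined.

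The one firm measure of size is the fourfold rise in the nominal FDR level. The rise from 0.05 to 0.20 in the chance of a false call, and the 0.158 after an empty first list, rest on one Benjamini-Hochberg family, a complete null, independent taxa and no averaging. A study-specific figure cannot be given, because the document states neither the FDR family nor the variation between instances. The conclusion about the label does not depend on that figure.

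The null covers only the abundance tests. The Data Analysis section also plans alpha and beta diversity, for which the Statistical Analysis Plan text gives no result.

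**What to change.** - State as the main result that no taxa were significant at `padj` < 0.05 at the levels and contrasts tested.
- Relabel taxa with `padj` between 0.05 and 0.2 as post hoc, exploratory and not significant. List each with its level, contrast, effect estimate and `padj`. If the vendor's text must stay as quoted, put this in an accompanying statement.
- Document the FDR family actually used, the contrasts run and the number of taxa tested per level. FDR over one pooled family may be added as a sensitivity analysis but is not required.
- In the listing, do not describe Day 120 contrasts as one month after stopping. Under Materials and Methods, patients without significant improvement at the second visit continue treatment to Day 120, and the model "taxon_abundance ~ Treatment_Cohort*Timepoint + (1|SubjectID)" has no term for stopping. Isolating that effect would need a new model or subset and is outside this fix.

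The cost is wording plus details the analyst should already hold, with no re-analysis. The few taxa lose the label significant but stay in the report as leads for further study.
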